10.3 Reporting of Adverse Events

At each contact with the subject, the investigator must seek information on AEs by specific questioning and, as appropriate, by examination. Information on all AEs should be recorded immediately in the source document and also in the appropriate AE module of the eCRF. All clearly related signs, symptoms, and abnormal diagnostic procedures results should recorded in the source document, though they should be grouped under one diagnosis.

All AEs occurring during the study period must be recorded on the appropriate eCRFs. The clinical course of each event should be followed until resolution, stabilization, or until it has been determined that the study treatment or participation is not the cause. Serious AEs that are still ongoing at the end of the study period must be followed up to determine the final outcome. Any serious AE that occurs after the study period and is considered to be possibly related to the study treatment or study participation should be recorded and reported immediately no later than 24 hours after awareness of the event.

10.3.1 *Study Sponsor Notification by Investigator*

In the event of any fatal or life-threatening SAE, the investigator must inform SK Life Science, Inc. (SKLSI) designee QDS by telephone immediately. Any non-fatal or non-life-threatening SAE, regardless of expectedness or causality, must be reported on the SAE Report Form by scanned and emailed to SKLSI's designee QDS within 24 hours of the investigator's or any other study center personnel's knowledge of the event as described below.

A completed SAE Report Form, the AE record, pertinent medical records, and the Concurrent Medication record from the source documents should be scanned and emailed to SKLSI's designee QDS within 24 hours of the investigator's or any study center personnel's knowledge of a serious event. An updated SAE Report Form should be forwarded to SKLSI's designee QDS within 24 hours of receipt of new/updated information. The SAE Reporting Requirements and contact information are outlined in Table 12.

Seizures in this subject population are anticipated. Therefore, seizures, in and of themselves, will not be considered adverse events. Seizures to be considered adverse events will include those occurring with a measurable increase over the subject's typical seizure frequency or duration; or multiple seizures in a pattern distinguishable from the usual seizure pattern.

Table 12. Serious Adverse Event Reporting Requirements

Type of SAE	Reporting	Reporting	Email address, Telephone Number,
-------------	-----------	-----------	----------------------------------

- Study center
- Subject number
- A description of the event
- Date of onset
- Current status
- Whether study treatment was discontinued
- The reason why the event is classified as serious
- Investigator assessment of the association between the event and study treatment

Within the following 48 hours, the investigator must provide further information on the serious AE in the form of a written narrative. This should include a copy of the completed SAE form, and any other diagnostic information that will assist the understanding of the event. Significant new information on ongoing serious AEs should be provided promptly to the study Sponsor.

10.3.2 *Ethics Committee/Institutional Review Board Notification by Investigator*

Reports of all serious AEs (including follow-up information) must promptly be submitted to the Ethics Committee/Institutional Review Board (EC/IRB). Copies of each report and documentation of EC/IRB notification and receipt will be kept in the clinical investigator's binder.

10.3.3 *Regulatory Authority Notification of IND Safety Reports by Sponsor*

The study Sponsor must notify the FDA and all participating investigators in an IND safety report of potential serious risks from clinical trials as soon as possible but in no case later than 15 calendar days after the Sponsor determines that the information qualifies for reporting. This includes any suspected adverse reaction that is both serious and unexpected (SUSAR).

The study Sponsor must notify the FDA of any unexpected fatal or life-threatening suspected adverse reaction as soon as possible but no later than 7 calendar days from the Sponsor's initial receipt of the information.

If a previous AE that was not initially deemed reportable is later found to fit the criteria for reporting, the study Sponsor will submit the AE in a written report to the FDA as soon as possible, but no later than 15 calendar days from the time the determination is made.

The notification of other Regulatory Authorities follows the same procedure and timeframe, per ICH Guidance, as for the FDA.

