10 SAFETY AND ADVERSE EVENTS

10.1 Definitions

10.1.1 *Adverse Events*

An adverse event (AE) is any symptom, sign, illness, or experience that develops or worsens in severity during the course of the study. Intercurrent illnesses or injuries should be regarded as AEs. Abnormal results of diagnostic procedures are considered to be AEs if the abnormality:

- Results in study withdrawal
- Is associated with an SAE
- Is associated with clinical signs or symptoms
- Leads to additional treatment or to further diagnostic tests
- Is considered by the investigator to be of clinical significance

10.1.2 *Serious Adverse Event*

AEs are classified as serious or non-serious. A *serious adverse event* is any AE that is:

- Fatal
- Life-threatening
- Requires or prolongs hospital stay
- Results in persistent or significant disability or incapacity
- A congenital anomaly or birth defect
- An important medical event

Important medical events are those that may not be immediately life threatening but are clearly of major clinical significance. They may jeopardize the subject and may require intervention to prevent one of the other serious outcomes noted above. For example, drug overdose or abuse, a seizure that did not result in inpatient hospitalization, or intensive treatment of bronchospasm in an emergency department would typically be considered serious.

10.1.3 *Suspected Adverse Reaction*

Suspected adverse reaction means any AEs for which there is a reasonable possibility that the drug cause the AE. For the purpose of investigational new drug (IND) safety reporting, “reasonable possibility” means there is evidence to suggest a causal relationship between the drug and AE. Suspected adverse reaction implies a lesser degree of certainty about causality than adverse reaction, which means any AE caused by a drug.

All AEs that do not meet any of the criteria for seriousness should be regarded as *non-serious AEs*.

10.1.4 *Adverse Event Reporting Period*

The study period during which AEs must be reported is normally defined as the period from the initiation of any study procedures (Visit 1) to the end of the study treatment follow-up. For this study, the AE reporting period is defined as 30 days following the last administration of study treatment for SAEs. For all other AEs, reporting period is defined as 14 days following the last administration of study treatment.

10.1.5 *Preexisting Condition*

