A preexisting condition is one that is present at the start of the study. A preexisting condition should be recorded as an AE if the frequency, intensity, or the character of the condition worsens during the study period.

At Visit 1 any clinically significant abnormality should be recorded as a preexisting condition. At the end of the study, any new clinically significant findings/abnormalities that meet the definition of an AE must also be recorded and documented as an AE.

Post-study Adverse Events

All unresolved AEs should be followed by the investigator until the events are resolved, the subject is lost to follow-up, or the AE is otherwise explained. At the last scheduled visit, the investigator should instruct each subject to report any subsequent event(s) that the subject, or the subject's personal physician, believes might reasonably be related to participation in this study.

The investigator should notify the study Sponsor of any death or AE occurring at any time after a subject has discontinued or terminated study participation that may reasonably be related to this study. The Sponsor should also be notified if the investigator should become aware of the development of cancer or of a congenital anomaly in a subsequently conceived offspring of a subject who has participated in this study.

Abnormal Laboratory Values

A clinical laboratory abnormality should be documented as an AE if *any one of the following* conditions is met:

- The laboratory abnormality is not otherwise refuted by a repeat test to confirm the abnormality.
- The abnormality suggests a disease and/or organ toxicity.
- The abnormality is of a degree that requires active management (eg, change of dose, discontinuation of the drug, more frequent follow-up assessments, further diagnostic investigation).

Hospitalization, Prolonged Hospitalization, or Surgery

Any AE that results in hospitalization or prolonged hospitalization should be documented and reported as a serious AE unless specifically instructed otherwise in this protocol. Any condition responsible for surgery should be documented as an AE if the condition meets the criteria for an AE.

Neither the condition, hospitalization, prolonged hospitalization, nor surgery are reported as an AE in the following circumstances:

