- Hospitalization or prolonged hospitalization for diagnostic or elective surgical procedures for a preexisting condition. Surgery should **not** be reported as an outcome of an AE if the purpose of the surgery was elective or diagnostic and the outcome was uneventful.
- Hospitalization or prolonged hospitalization required to allow efficacy measurement for the study.
- Hospitalization or prolonged hospitalization for therapy of the target disease of the study, unless it is a worsening or increase in frequency of hospital admissions as judged by the clinical investigator.
- An Emergency Room visit is not considered hospitalization.

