8.1 Screening and Baseline

At the time of enrollment in the study, all subjects will sign the informed consent.

Demographic data (Date of Birth, Sex, Race and Ethnicity), characterizing enrolled subjects will be collected on the Demographics eCRF.

Height and weight at baseline will be recorded on the Vital Signs eCRF.

The subject's date of past and present medical conditions, prior to study enrollment, will be recorded on a Medical History eCRF. Medical history data will include the Body System, verbatim text, start date, and end date or ongoing.

The subject's epilepsy/seizure history including past and current seizures will be recorded on an Epilepsy/Seizure History eCRFs. Seizure identification and Etiology data will also be collected.

Physical Examination at screening (full examination) will be recorded on the Physical Exam eCRF. These data will include Body System, a normal/abnormal indication, and a description of the abnormality.

All non-AED medications taken by the subject up to the first dose of the study drug will be recorded on the Prior and Concomitant Medications eCRF. These data will include the verbatim medication name, indication for use, dose, route, frequency, start date, and end date or ongoing indication.

A full neurologic evaluation examination will also be performed at screening and recorded on the eCRF. If the subject has not had a recent (within the last 10 years) CT or MRI, one will be performed and entered on the eCRF. An electrocardiogram (EEG) may also be performed and entered on the eCRF. At baseline visit, a brief neurologic examination may be performed (if needed).

Twelve-lead ECGs overall interpretation and results will be collected at screening and will be entered on an eCRF.

Clinical laboratory evaluations (including blood and urine) will be collected at screening and results will be returned electronically for inclusion in the clinical database.

Serum or urine pregnancy test results, where applicable, will be entered into the eCRF.

The baseline version of the Columbia Suicide Rating Scale (C-SSRS) will be assessed at Visit 1 and entered on the eCRF.

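### Protocol 10.3.1 and 10.1.5 give different answers on whether a single first seizure of a new or more severe type is an adverse event, and no text says which prevails

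*Protocol*

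**What the plan says.** Protocol 10.3.1 (Study Sponsor Notification by Investigator) starts from the fact that seizures are expected in this population and sets a default: "Therefore, seizures, in and of themselves, will not be considered adverse events". The next sentence opens the list of exceptions: "Seizures to be considered adverse events will include those occurring with a measurable increase". The increase is judged against what is usual for that subject, and the sentence closes with the cases it names: "typical seizure frequency or duration; or multiple seizures in a pattern distinguishable from the usual seizure pattern".

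Three passages in Protocol 10.1 bear on the same events:

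- 10.1.1 defines an AE as "any symptom, sign, illness, or experience that develops or worsens in severity during the course of the study".
- 10.1.5 states: "A preexisting condition should be recorded as an AE if the frequency, intensity, or the character of the condition worsens during the study period".
- 10.1.2, explaining important medical events, lists "a seizure that did not result in inpatient hospitalization" among examples that would typically be considered serious.

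The hospitalization rule in the same section exempts admissions for the target disease, "unless it is a worsening or increase in frequency of hospital admissions as judged by the clinical investigator".

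The SAP adds no seizure-specific rule. Section 8.2.1 takes AEs as recorded on the Adverse Events eCRF, and 13.1 restricts the summary tables to treatment-emergent AEs. On the baseline side, SAP 8.1 describes an epilepsy and seizure history and adds: "Seizure identification and Etiology data will also be collected".

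**The concern.** Every subject enters with epilepsy, so epilepsy is a preexisting condition for the whole study population. Two sections of the protocol set the test for when it has become an AE, and the tests differ. 10.1.5 looks at frequency, intensity and character. 10.3.1 names frequency and duration, and reaches a change of pattern only through multiple seizures.

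Long-term safety is a stated objective, and AE incidence is a main output. There is no control arm, and neither Protocol 6.2.2 nor SAP 7.2 lists a seizure measure among the safety endpoints. The flow chart in SAP Appendix 1 has seizure history at Visit 1 and no seizure assessment afterwards, and the visit lists in Protocol 9.1 agree with it. If an episode of seizure worsening is not entered as an AE, no other planned table shows it as seizure worsening.

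The protocol itself treats severity as distinct from frequency. Its argument for an add-on design in 4.2 cites the risk that both may be exacerbated when long-term therapy is withdrawn. In this study concomitant drugs may be removed and YKP3089 is tapered at withdrawal, so the distinction has practical relevance.

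**Working it through.** No arithmetic applies: the point compares recording rules, and the documents give no figure to reproduce. The check takes one event through each rule.

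**Test event.** One first seizure of a type the subject has not had before, or clearly more severe than usual. Its duration is usual, overall seizure frequency does not rise, and there is no hospital admission.

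| Rule | Criterion | Result for the test event |
|---|---|---|
| Protocol 10.1.1 | Develops, or worsens in severity | AE |
| Protocol 10.1.5 | Frequency, intensity or character worsens | AE, by intensity or character |
| Protocol 10.3.1, first exception | Measurable increase in frequency | Not met on overall frequency |
| Protocol 10.3.1, second exception | Measurable increase in duration | Not met |
| Protocol 10.3.1, third exception | Multiple seizures in a distinguishable pattern | Not met: one seizure |
| Protocol 10.3.1, default | Seizures in themselves are not AEs | Not an AE, if the list is read as complete |

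**Precedence.** The visible text does not say whether 10.3.1 overrides 10.1.5, or whether 10.1.5 still applies to seizures.

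**How wide the gap is.** The following neighbouring events are covered:

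- A prolonged seizure meets the duration exception.
- A cluster in a new pattern meets the third exception.
- An admission that represents worsening stays reportable under the hospitalization rule. This depends on the investigator's judgement, and an emergency room visit does not count as hospitalization.

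The comparison also runs the other way: 10.3.1 names duration, which 10.1.5 does not. What is left uncovered is the single seizure of new type or greater intensity described above.

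**Serious events.** 10.1.2 defines a serious AE as an AE meeting a seriousness criterion, so an event judged under 10.3.1 not to be an AE never reaches that step. Yet 10.1.2 itself uses a seizure without admission as an example of a typically serious event. The two sections therefore also conflict on seriousness.

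**Effect on the tables.** An event not entered on the Adverse Events eCRF cannot enter the treatment-emergent or serious AE tables of SAP 13.1, and no SAP rule would recover it.

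**The case against.** The strongest reply is that 10.3.1 does not state a closed list. A reader might infer that it counts only the named cases, but the wording is that AEs will include them. The exclusion covers seizures in and of themselves, on the ground that seizures are anticipated, and a subject's first seizure of a new type is arguably not the anticipated one. An investigator could also treat it as a measurable increase from a typical frequency of zero for that type. 10.1.1 and 10.1.5 remain in force, and nothing in 10.3.1 says that it displaces them. A separate rule for expected disease events is a deliberate and ordinary choice.

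Much of this stands. The text does not forbid recording the event, and a careful investigator may well record it. However, the list follows directly on a blanket exclusion, so reading it as the set of exceptions is natural. With about 80 to 110 sites in several countries, both readings are available. That inconsistency is the defect, and it does not require the closed reading to be the correct one.

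A reader might also infer that the AE form is the only place where seizure worsening could appear. That goes too far. Reasons for unscheduled visits and calls (Protocol 9.2), concomitant AED administration (SAP 8.2.2) and reasons for withdrawal (SAP 11.1) can give indirect signals. None of them replaces an AE entry, because none is planned to be tabulated as seizure worsening.

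**Conclusion.** The protocol contains an unresolved conflict. A single first seizure of a new or more severe type, of usual duration and without a rise in overall frequency, is an AE under 10.1.1 and 10.1.5 but meets no exception named in 10.3.1. Sites can record it differently, and it can be missing from the treatment-emergent and serious AE tables. The example in 10.1.2 adds a second inconsistency.

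The size cannot be estimated from the documents. A reader might assume a rate such as 1% to 3% of the 1,000 subjects (0.01 × 1,000 = 10 to 0.03 × 1,000 = 30) and infer 10 to 30 lost events. No passage supports that rate, and losing all of them would require every site to read the list in 10.3.1 as complete in every case.

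The conclusion rests on two things: that no text available for review sets an order of precedence, and that some sites will follow 10.3.1 as it is written. It is a narrow ambiguity, but it affects a main safety output and is cheap to remove, so it should be corrected.

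**What to change.** Reconcile the passages with three short changes:

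1. State in Protocol 10.3.1 that 10.1.5 also applies to seizures, so that worse intensity or character is an AE.
2. Name in 10.3.1, as an AE, any seizure, even a single one, of a type not in the seizure history recorded at Visit 1. The reference is already collected (SAP 8.1) and summarized by type (SAP 11.6), so no new data item is needed.
3. Align the seizure example in 10.1.2 with 10.3.1, so that it is clear when a seizure without admission is an AE and can then be assessed for seriousness.

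Intensity is better handled by the cross-reference than by a separate trigger. The documents describe a recorded baseline for seizure type but none for intensity, so a new intensity threshold would itself be applied unevenly.

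The cost is a short amendment, which under Protocol 13.6 needs prior submission to and written approval from the ethics committees, plus a site memo. A few more seizure AEs will be reported.

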10.4 Withdrawal of Subject from Study

Subjects may be withdrawn from the study prior to completion of the study if:

- Consent is withdrawn by the subject
- The subject fails to adhere to the protocol requirements
- An intolerable AE is experienced
- The subject becomes pregnant
- The subject is lost to follow-up

When a subject is withdrawn, the discharge procedures must be performed. The reason(s) for the withdrawal must be documented in the subject's eCRF.

11 DATA HANDLING PROCEDURES

11.1 Data Handling and Record Keeping

11.1.1 Confidentiality

Information about study subjects will be kept confidential and managed according to the requirements of the Health Insurance Portability and Accountability Act (HIPAA). Those regulations require a signed subject authorization informing the subject of the following:

- What protected health information (PHI) will be collected from subjects in this study
- Who will have access to that information and why
- Who will use or disclose that information
- The rights of a research subject to revoke their authorization for use of their PHI

The subjects will be told that representatives of the Sponsor, IRB/IEC, or regulatory authorities may inspect their medical records to verify the information collected and that all personal information made available for inspection will be handled in strictest confidence and in accordance with local data protection laws.

In the event that a subject revokes authorization to collect or use PHI, the investigator, by regulation, retains the ability to use all information collected prior to the revocation of subject authorization. For subjects who have revoked authorization to collect or use PHI, attempts should be made to obtain permission to collect at least vital status (ie, that the subject is alive) at the end of his or her scheduled study period.

11.1.2 *Source Documents*

Source data is all information, original records of clinical findings, observations, or other activities in a clinical trial necessary for the reconstruction and evaluation of the trial. Source data are contained in source documents. Examples of these original documents and data records include hospital records; clinical and office charts; laboratory notes; memoranda; subjects' diaries or evaluation checklists; pharmacy dispensing records; recorded data from automated instruments; copies or transcriptions certified after verification as being accurate and complete; microfiches; photographic negatives; microfilm or magnetic media; x-rays; subject files; and records kept at the pharmacy, at the laboratories, and at medico-technical departments involved in the clinical trial.

11.1.3 *Electronic Case Report Forms*

The eCRF is the primary data collection instrument for the study. All data requested on the eCRF must be recorded. All missing data must be explained. Details of the completion of the eCRF will be included in a data entry manual.

11.1.4 *Records Retention*

In compliance with the ICH/GCP guidelines, the investigator/institution will maintain all eCRFs and all source documents that support the data collected from each subject, as well as all study documents as specified in ICH/GCP Section 8, Essential Documents for the Conduct of a Clinical Trial, and all study documents as specified by the applicable regulatory requirement(s).

The investigator/institution will take measures to prevent accidental or premature destruction of these documents. Essential documents must be retained until at least 2 years after the last approval of a marketing application in an ICH region and until there are no pending or contemplated marketing applications in an ICH region or until at least 2 years have elapsed since the formal

